### 3.4 What is the age range of participants?

>18 years old. Controls will be matched to age and gender of the POTS and LCS cohorts

### 3.5 If this research involves children under 18 years of age, describe how the researcher/s comply with the [University's Child-Safe Environment Policy](#):

See *National Statement* Chapter 4.2. Specific requirements for research activities involving children are highlighted in Section 2.4 of the [University's Child-Safe Environment Policy](#).

N/A

### 3.6 What is the participant selection and exclusion criteria?

See *National Statement Chapter 3.1.14 – 3.1.15*.

### **Inclusion Criteria**

Cohort 1 (LCS): Adults aged  $\geq 18$  years old (male or female); Able to provide written informed consent; previous SARS-CoV-2 infection (As some Australians contracted SARS-CoV-2 in countries that did not undertake testing in the early stages of the pandemic, some participants will not have a diagnosis by PCR. Inclusion with physician confirmed Long Covid is consistent with worldwide research practices for Long Covid studies); continuing chronic symptoms persisting for  $\geq 3$  months post-acute COVID-19 infection and not attributable to an alternative disease state.

Cohort 2 (POTS): Adults aged  $\geq 18$  years old (male or female); POTS diagnosis; Able to provide written informed consent; Diagnostic criteria for POTS met as per the following: 1. sustained heart rate elevation of  $\geq 30$  beats/min within 10 minutes. 2. No other secondary cause of these symptoms. 3. Absence of orthostatic hypotension 4. Symptomatology present for greater than 3 months

Cohort 3 (Healthy Control): Otherwise, healthy adults aged  $\geq 18$  years old (male or female); Able to provide written informed consent; absence of POTS diagnosis or previous SARS-CoV-2 infection.

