## SECTION 2: NATURE OF THE PROJECT

### 2.1 Aims of the project:

Discuss in standard English the main research aims/hypotheses to be investigated.

The primary objective of this study is to:

[1] Assess the prevalence of POTS in those with LCS, using a standardised and detailed autonomic testing protocol

The secondary objectives of this study include:

[2] Characterising the neuroendocrine/inflammatory/immune biomarker profile of those with LCS(+)/POTS/LCS(-)/POTS and POTS and compare to matched, healthy controls

[3] Determining the impact of LCS with and without POTS and POTS on quality of life & symptom scores, cognitive function and psychological well-being and compare to matched, healthy controls

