### 2.3 Background to the project:

Briefly discuss any previous research of relevance and cite no more than 4 key references.

Long COVID Syndrome (LCS) is a term now frequently utilized to describe the collection of chronic symptoms lingering at  $\geq 3$  months post-acute SARS-CoV-2 infection. Several studies detail the presence of multi-systemic chronic symptoms such as fatigue, reduced cognition, exercise intolerance, pain and tachycardia in this cohort. While much remains unknown regarding LCS, involvement of the autonomic nervous system has been suggested.

The Office for National Statistics, UK have found that as many as 1 in 10 individuals are likely to suffer these symptoms post SARS-CoV-2 infection consistent with LCS. With more than 108 million global cases of SARS-CoV-2 infection (as of February 13th 2021, Johns Hopkins Coronavirus Resource Center), there are potentially a high burden of LCS cases. Consequently, detailed characterization of this cohort of LCS patients is important as a high proportion of these individuals remain symptomatic with significant disability and unable to return to work.

Postural orthostatic tachycardia syndrome (POTS) is a heterogenous disorder characterized by chronic and disabling symptomatology that predominately affects young women of child bearing age. POTS onset has a reported association with antecedent viral illness as well as concomitant autoimmune disease. Onset of this multisystemic disorder has been described in a recent case report after SARS-CoV-2 infection. The pathophysiology remains unknown but may include post-viral autoimmunity, increased central sympathetic outflows, deconditioning/hypovolemia or neuro-endocrine related. Indeed, inflammatory biomarkers and

adrenergic and cholinergic antibodies have been reported in POTS and are of interest in the pathogenesis of post viral onset of this syndrome and the interplay with inflammatory pathways and neuroendocrine dysfunction.

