### **Exclusion:**

Non-consent for participation in study; pregnancy or lactation; other known causes of autonomic dysfunction; co-morbidities such as Type 1 Diabetes, Parkinson's disease, multiple sclerosis, alcoholism, drug addiction, malignant neoplasm, recent cerebrovascular accident or transient ischaemic attack, acquired brain injury; significant surgery within the last 3 months; unavailability for completion of all assessments as per the study protocol; non-English speaker; terminally ill with life expectancy  $< 12$  months.

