#### Attachment 4: Social Media Admin Email and Advert

Dear Social Media Administrators,

We are researchers at the University of Adelaide who are investigating the cardiovascular, immune and inflammatory profile of those with 'Long Covid'. We aim to compare results of blood tests and heart function with healthy controls as well as with people who have Postural Orthostatic Tachycardia Syndrome (POTS). Long Covid Syndrome is not yet well understood. We hope that this study will reveal underlying reasons for the extended fatigue, brain fog and cardiac and respiratory symptoms that these people suffer after Covid-19 infection. This study has ethics approval from The University of Adelaide H-2021-053

We would greatly appreciate your assistance in recruiting eligible study participants for this study by placing an advertisement in your social media support group. We understand that you may have questions in relation to the study that you would like to pose before making a decision. You are welcome to email us in return to discuss further. Below I have attached a copy of the advertisement we would like to place on your support page.

Regards,

Associate [name]  
[name] (PhD Student): [contact]  
[name]  
[name]  
[name]

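### Cohort 2 has no SARS-CoV-2 criterion, so POTS that began after COVID-19 can enter the POTS group and weaken the secondary long COVID–POTS comparison

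*Protocol*

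**What the plan says.** Section 3.6 of the protocol defines Cohort 2 by age, consent and "POTS diagnosis; Able to provide written informed consent; Diagnostic criteria for POTS met as per the following". Four points follow: a sustained heart-rate rise, "No other secondary cause of these symptoms", no orthostatic hypotension, and symptoms for more than three months. SARS-CoV-2 history is not among them. In the same section Cohort 3 requires "absence of POTS diagnosis or previous SARS-CoV-2 infection". The exclusions common to all cohorts include "other known causes of autonomic dysfunction" but do not name SARS-CoV-2 or long COVID syndrome (LCS).

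Sections 3.3 and 3.7 recruit 34 consecutive patients from a specialist POTS clinic, with no filter on date of onset or infection history. Section 1.3 places the project between March 2021 and March 2025.

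The background (2.3) links POTS onset to antecedent viral illness and adds: "Onset of this multisystemic disorder has been described in a recent case report after SARS-CoV-2 infection".

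Secondary objective [2] in section 2.1 concerns the "biomarker profile of those with LCS(+)/POTS/LCS(-)/POTS and POTS and compare to matched, healthy controls". Objective [3] uses the same groups for quality of life, cognition and psychological well-being. Attachment 4 says the investigators aim to "compare results of blood tests and heart function with healthy controls as well as with people who have Postural Orthostatic Tachycardia Syndrome". Attachment 3 tells POTS clinic patients that the study looks for similarities between the two conditions.

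**The concern.** The protocol treats LCS with POTS and POTS as separate groups and tells recruits that they will be compared. That comparison is informative only if the POTS group stands apart from post-COVID illness. Infection status is controlled in the healthy comparator but not in the POTS comparator.

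A patient whose POTS began after COVID-19 could be seen at the clinic, be diagnosed, and be enrolled in Cohort 2. That patient may be clinically close to a Cohort 1 participant with POTS. Each such enrolment moves the POTS group toward the LCS-with-POTS group. A finding of similarity, which is what Attachment 3 says is being looked for, could then come partly from who was enrolled.

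**Working it through.** **1. What the eligibility text says about SARS-CoV-2 (section 3.6)**

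| Group | Condition on infection |
|---|---|
| Cohort 1 (LCS) | Previous infection required |
| Cohort 2 (POTS) | None stated |
| Cohort 3 (controls) | No previous infection |
| Common exclusions | None naming SARS-CoV-2 |

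**2. Do the generic criteria close the gap?** Two could be tried.

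- "No other secondary cause of these symptoms" would exclude post-COVID POTS only if the infection counts as a secondary cause. Section 2.3 treats viral illness as an antecedent of POTS, not as an alternative diagnosis.
- "other known causes of autonomic dysfunction" applies to every cohort. Read as covering COVID-19, it would also remove the LCS patients with POTS whom the study sets out to find.

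Neither therefore works reliably. Two investigators could decide the same case differently.

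**3. The plan's own sizing figures (section 3.3)**

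- Prevalence: n = 1.96² × 0.10 × 0.90 / 0.05² = 138.3, so 139. This agrees with the protocol.
- POTS versus control: difference 19 bpm, SDs 15.5 and 19.4, 15 per group, two-sided alpha 0.05. Standard error = √(15.5²/15 + 19.4²/15) = 6.41. The noncentral t with Satterthwaite degrees of freedom gives power 0.815, against 80% stated.
- At the assumed 10%, Cohort 1 should yield about 0.10 × 150 = 15 participants with LCS and POTS.

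No figure in the protocol sizes the LCS-with-POTS versus POTS comparison.

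**4. Dilution.** Let f be the share of Cohort 2 whose POTS began after COVID-19. The protocol gives no value, so f is an assumption. Suppose these patients have the LCS-with-POTS mean, μL, and the rest have μP. The Cohort 2 mean is (1−f)μP + fμL, and the expected difference is

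μL − [(1−f)μP + fμL] = (1−f)(μL − μP).

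The sample needed for equal power rises by 1/(1−f)². To illustrate power, take 15 versus 34 patients with equal SDs. A true difference of 0.90 SD then has 80% power at f = 0.

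| f | Difference retained | Sample multiplier | Power | Power with mixture variance |
|---|---|---|---|---|
| 0 | 100% | 1.00 | 80% | 80% |
| 10% | 90% | 1.23 | 71% | 70% |
| 20% | 80% | 1.56 | 61% | 60% |
| 30% | 70% | 2.04 | 50% | 48% |

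**5. What happens if post-COVID clinic patients are moved to Cohort 1.** They already have POTS, so each one adds a case to the prevalence numerator. Take 10% prevalence among the other participants and 150 places in all. The counts below are about 20%, 30% and 50% of 34.

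- 7 moved: (143 × 0.10 + 7)/150 = 14.2%
- 10 moved: (140 × 0.10 + 10)/150 = 16.0%
- 17 moved: (133 × 0.10 + 17)/150 = 20.2%

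With 10 moved, the 6-point bias already exceeds the planned 5-point precision.

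**The case against.** The strongest reply is that the weakened contrast is not the formal one. Objectives [2] and [3] name healthy controls as the comparator, and Cohort 2 was sized for a heart-rate difference from healthy people. A patient with post-COVID POTS still has POTS, so the (1−f) formula does not describe POTS versus controls. This stands, and it limits the point to a secondary comparison that rests on the group structure of section 2.1 and on Attachments 3 and 4.

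The size is also assumed. No f is given, and section 2.3 cites only one case report of POTS after SARS-CoV-2. Cohort 2 is described as existing treated patients (3.1), screened from a clinic database (3.9), which may keep f low. March 2025 is the estimated completion date, not a stated end of recruitment. The formula further assumes that post-COVID POTS resembles LCS with POTS, which is partly what the study is investigating. If the resemblance is only partial, the dilution is smaller.

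A reader might infer that a post-COVID POTS patient certainly meets every Cohort 2 criterion. The text does not support that: an investigator could apply either generic criterion to such a patient. The supportable statement is that the criteria are ambiguous and may let the patient in.

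A reader might also infer that the main result is compromised. It is not, because POTS prevalence is estimated in Cohort 1 alone.

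Finally, a sensitivity analysis could be left to a statistical analysis plan. It would need onset and infection dates, however, and the history items listed in section 3.16 do not name them.

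**Conclusion.** The point holds as a gap in Cohort 2 eligibility that bears on a secondary comparison. The protocol controls SARS-CoV-2 history in the healthy group and leaves it open in the POTS group, and the generic criteria do not settle the matter. Followed as written, the plan can place post-COVID POTS in the POTS group and shrink its difference from LCS with POTS.

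The expected loss equals f: 10%, 20% or 30% of the true difference at those shares. This rests on an assumed f and on the affected patients resembling LCS with POTS. The power figures also assume 15 versus 34 patients, equal SDs and a true difference of 0.90 SD, none of which the protocol states for this comparison. The primary prevalence estimate is unaffected, and the stated comparisons with healthy controls are not diluted in this way.

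**What to change.** - Add to the Cohort 2 inclusion criteria that POTS onset predates any known SARS-CoV-2 infection and that the patient does not have LCS.
- Record the dates of POTS onset and of any SARS-CoV-2 infection in the medical history taken under section 3.16.
- For anyone already enrolled, repeat the POTS contrasts without patients whose POTS began after infection.
- Do not move POTS-clinic patients into Cohort 1. They would be selected on the primary outcome and would bias the prevalence upward.

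The cost is a slightly smaller clinic pool for the 34 places and one extra history field. The criterion depends on known infection, so unrecognised infections would remain a residual limit.

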### **Exclusion:**

Non-consent for participation in study; pregnancy or lactation; other known causes of autonomic dysfunction; co-morbidities such as Type 1 Diabetes, Parkinson's disease, multiple sclerosis, alcoholism, drug addiction, malignant neoplasm, recent cerebrovascular accident or transient ischaemic attack, acquired brain injury; significant surgery within the last 3 months; unavailability for completion of all assessments as per the study protocol; non-English speaker; terminally ill with life expectancy  $< 12$  months.

### **3.7 Where will participants be recruited or sourced from?**

Any use of snowball sampling for recruitment should only be in the passive form. That is participants may be asked to discuss the research with friends/contacts who they think may be interested in volunteering to be participants. Those new participants should then contact the research team to volunteer.

Participants will be recruited through social media forums that pertain to support of those with LCS. Administrators of social media platforms for LCS will be approached by senior investigators for permission to post information about the study with contact details for researchers. We recognised the selection bias associated with this method of recruitment, however given the extraordinary nature of the current pandemic and the lack of understanding of LCS and its associated diagnosis and aetiology, it would seem that this bias is justified by the urgent requirement for preliminary understanding of the condition. As this study looks to explore immune, inflammatory and cardiovascular changes rather than efficacy of interventions, the use of convenience sample is more tolerable.

In addition, consecutive patients with POTS who attend [name] practice and The University of Adelaide, Centre for Heart Rhythm Disorders will be recruited. Potential participants may be approached by a member of the clinic/study staff via email introducing the study and providing the plain language patient information sheet explaining the purpose of the study. Healthy controls will be recruited through flyers and posters placed within The University of Adelaide health and education campuses. In addition, healthy controls referred to CHRDC/CVC for investigation of heart arrhythmia (but found to have none) will be recruited via the above mentioned flyers. Advertisements will be placed on the SAHMRI and University of Adelaide facebook sites as per attachment 5.

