### 3.3 What is the number of participants?

Cohort One (LCS): 150 consecutive patients with LCS will be recruited from various social media and LCS support group platforms.

Cohort Two (POTS) 34 consecutive patients with POTS will be recruited from a speciality POTS clinic run by [name] who is an Assoc/Prof at The University of Adelaide, Centre for Heart Rhythm Disorders

Cohort Three (Controls): 34 healthy, matched age and gender controls will be recruited from University and private medical campuses.

A base sample size calculation can be made using the formula:  $n = (t^2 \times p(1-p)) / m^2$ , where  $t$ =confidence level at 95%,  $p$ =estimated prevalence of POTS within an LCS sample and  $m$  is the relative precision. Using this formula, a sample size of 139 provides sufficient statistical power to estimate a proportion (10% POTS amongst LCS) with a precision of 5% at the 95% confidence level. The number is increased to 150 to allow for withdrawal from the study.

From Walker et al. 2013 paper, the following information was obtained: at 30 minutes of orthostatic time, Stand healthy group (N=15) had mean orthostatic change in heart rate 26 bpm + SE=4 (SD=SE\*SQRT(N) = 15.5) and the Stand POTS group (N=15) had mean orthostatic change in heart rate 45 bpm + SE=5 (SD=SE\*SQRT(N) = 19.4). Using a two-sample Satterthwaite t Test assuming unequal variance, with alpha=0.05, two-sided test and SD=15.5 and 19.4, it was found that there was 80% power to detect a mean difference of 45-26=19 when using a sample size of N=15 per group. If there is expected to be 20% loss to follow up, then a total of  $(20/9)*30=66.66$  so N=34 is required in each group (N=68 in total) The statistical software used was SAS 9.4 (SAS Institute Inc., Cary, NC, USA).

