#### LCS- Social Media Advert

**Volunteers wanted for a study looking at the cardiovascular, immune and inflammatory function of those with "Long Covid Syndrome" and Postural Orthostatic Tachycardia Syndrome (POTS). Please contact [name] on [[contact]](mailto:[contact]) for more details.**

THE UNIVERSITY  
of ADELAIDE

**This study involves 2 visits for cardiovascular testing either in Melbourne or Adelaide. These tests will take approximately 2-3 hrs and will also include blood and urine samples.**

This study has ethics approval from The University of Adelaide, Human Research Ethics Committee H-2021-XXXX

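### POTS prevalence in Long COVID is the primary objective, but LCS volunteers answer adverts that name POTS, so the estimate is likely, though not certain, to be too high

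*Protocol*

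**What the plan says.** Protocol section 2.1 gives one primary objective: "Assess the prevalence of POTS in those with LCS, using a standardised and detailed autonomic testing protocol". Biomarkers, quality of life and cognition are secondary. Section 3.3 sizes the LCS cohort only for the primary objective, "to estimate a proportion (10% POTS amongst LCS) with a precision of 5% at the 95% confidence level".

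On where the cohort comes from, section 3.3 says "150 consecutive patients with LCS will be recruited from various social media and LCS support group platforms", and section 3.7 says "Participants will be recruited through social media forums that pertain to support of those with LCS". The recruitment list in section 3.8 gives one route for LCS, the social media advertisement in Attachment 4. Under section 3.9 the person with LCS makes the first contact by answering that notice.

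The Attachment 4 advert asks for volunteers for a study of Long Covid "and Postural Orthostatic Tachycardia Syndrome (POTS). Please contact" the research team. The headline of the accompanying notice is the study title, with POTS first.

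Section 3.7 acknowledges that recruiting this way brings selection bias. It defends this on two grounds. The first is the urgent need for a preliminary understanding of LCS during the pandemic. The second is: "As this study looks to explore immune, inflammatory and cardiovascular changes rather than efficacy of interventions, the use of convenience sample is more tolerable".

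**The concern.** A prevalence estimate depends on who enters the sample. It is biased whenever the chance of entering differs between people with and without the condition. Here the condition being counted is named in the advert read by those deciding whether to be counted. Someone with LCS whose heart races on standing, or who has been told they have or may have POTS, has an extra reason to reply.

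The second ground in section 3.7 describes the study by its immune, inflammatory and cardiovascular aims and contrasts these with testing interventions. It does not mention prevalence. The first ground, urgency, may explain why support groups were used, but it does not explain why the advert has to name POTS.

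The word 'consecutive' in section 3.3 suits a clinic list, where everyone who attends can be enumerated. It does not suit an open advert with no known denominator. If 'prevalence' and 'consecutive' reach the report together, readers will take the figure and its interval as applying to LCS in general.

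**Working it through.** **1. The plan's own figure.** Inputs from section 3.3: p = 0.10, m = 0.05, 95% confidence (z = 1.96).

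n = z² p(1 − p)/m² = 3.8416 × 0.09/0.0025 = 138.3, rounded up to 139.

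This reproduces the stated 139, with m taken as 5 absolute percentage points. The increase to 150 allows for a loss of 1 − 139/150 = 7.3%. At n = 139 the half-width is 1.96 × √(0.09/139) = 4.99 points. This covers sampling error only and presumes a random sample of people with LCS.

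**2. Effect of outcome-related participation.** Let k be the probability that a POTS-positive person with LCS ends up in the sample, divided by that of a POTS-negative person. The documents do not give k, so the values below are assumptions. With true prevalence p, the expected observed proportion is

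q = kp/(kp + 1 − p).

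With p = 0.10:

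| k | q | Bias (points) | Coverage of the true 10%, n = 139 |
|---|---|---|---|
| 0.5 | 0.05/0.95 = 5.3% | −4.7 | 31% |
| 1 | 0.10/1.00 = 10.0% | 0 | 93% |
| 1.5 | 0.15/1.05 = 14.3% | +4.3 | 74% |
| 2 | 0.20/1.10 = 18.2% | +8.2 | 28% |
| 3 | 0.30/1.20 = 25.0% | +15.0 | under 1% |

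Coverage is the exact binomial probability that the nominal 95% Wald interval contains 10%. For k = 1.5, 2 and 3 the Wilson interval does no better: 57%, 15% and 0.2%.

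**3. When the bias equals the planned precision.** Setting q = 0.15 gives k = (0.15/0.85)/(0.10/0.90) = 1.59. A participation ratio of about 1.6 is enough to shift the estimate by the whole 5 points.

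**4. Sample size does not help.** At k = 2, Wald coverage falls from 28% at n = 139 to about 22% at n = 150. With n = 5000 and an observed 18.2%, the interval would be about 17.1% to 19.3%, narrower and still clear of 10%.

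**5. Filters acting the other way.** If the advert multiplies participation by r, and POTS-positive volunteers pass the later filters s times as often as others, then k = r × s. For r = 2, s = 0.8 gives k = 1.6 and q = 15.1%, while s = 0.5 gives k = 1 and q = 10%. For r = 3, s = 0.5 gives k = 1.5 and q = 14.3%.

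**The case against.** A reader might infer that the estimate is bound to be too high. The documents do not support that. They give no response ratio, and several rules could remove POTS-positive people. Section 2.5 bars anyone who cannot stop the listed heart-rate and fluid medicines. The inclusion criteria in section 3.6 require symptoms not explained by another disease. The exclusions there cover other known causes of autonomic dysfunction and people unavailable for every assessment. Attachment 4 asks for two visits, which may deter the most disabled. This stands: the direction is a judgement and the size is unknown. But these filters may themselves be related to the outcome. They add uncertainty and do not restore a representative sample.

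A reader might also infer that the protocol hides the problem. It does not. Section 3.7 states the selection bias openly and uses the term convenience sample, and the sentence in section 3.3 containing 'consecutive' also names social media as the source. The word may mean successive eligible respondents. The defect is a justification that does not reach the primary objective, plus one misleading term. The sample-size arithmetic is correct.

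The advert is also broader than POTS. Its eligibility text asks for more than three months of unexplained symptoms after Covid-19, and the email to group administrators leads with Long Covid. That softens the pull but does not remove it, since POTS is in both text and headline.

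Finally, neutral adverts would only postpone some of the self-selection, because the information sheet and telephone discussion precede consent. That is true, so neutral wording reduces the problem without curing it.

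**Conclusion.** The point holds in this form: the primary objective is a prevalence, the only listed LCS route is self-referral from adverts that name the outcome, and the argument that a convenience sample is more tolerable does not address prevalence. Upward bias is likely but not certain.

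For a true prevalence of 10%, the expected result runs from 14% to 25% for k between 1.5 and 3, and is about 5% if k = 0.5. Both the 10% and k are assumptions: the first is the protocol's planning value, and the second has no source in the documents. The planned 5-point precision is smaller than the bias for any k above about 1.6.

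Nothing here shows that the LCS sample is too small or that support-group recruitment must be abandoned. The protocol needs to limit what the primary result is said to describe, and to remove the avoidable part of the selection.

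**What to change.** 1. In Attachment 4, use neutral Long COVID wording in the LCS advert and its headline. Keep POTS testing disclosed in the information sheet, before consent.
2. At first contact, record whether the person has, or has been told they may have, POTS. Keep counts of enquiries, people screened and people enrolled. The medical history in section 3.16 may capture earlier diagnoses among those enrolled, but it does not cover people who enquire and go no further. Report the proportion overall and again without those with a prior or suspected diagnosis. Label the second a lower-side sensitivity figure, because it removes true cases, including POTS diagnosed after COVID. The analysis detail can sit in the statistical analysis plan, but the data must be collected from the start.
3. In section 3.3, replace 'consecutive' with 'volunteer' for the LCS cohort. State the primary result as the proportion meeting POTS criteria among self-referred support-group volunteers, and say that the 5-point precision covers sampling error only.
4. Rewrite the justification in section 3.7 so that it addresses prevalence: the likely direction of the bias, why its size is unknown, and the limit this places on interpretation.

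The cost is a minor ethics amendment, one screening question, a simple enquiry log and one extra reported proportion. Recruitment may be slower.
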